9.8. Safety Analyses

All patients in the safety population will be used in the safety analyses. Safety analyses will be summarized by treatment group as treated.

The treatment-emergent period will be defined as in [Section 7.1](#). For incomplete date of last dose of study drug that are missing the day of the month, the 15th of the month will be assumed in determining the treatment-emergent period.

9.8.1. Adverse Events

The severity of all adverse events is to be evaluated by the investigator based on the National Cancer Institute (NCI) Common Terminology Criteria for Adverse Events (CTCAE) version 4.0 or later. All adverse events will be coded to preferred term (PT) and system organ class (SOC) using MedDRA 14.1 or higher.

Treatment-emergent adverse events (TEAEs) are adverse events that started or worsened in severity during the treatment-emergent period.

Patients with multiple occurrences of events for a given PT, SOC, or overall will only be counted once at the worst severity and strongest relationship to study drug for each PT, SOC and overall, respectively.

Adverse event time-adjusted rates will be calculated as the number of occurrences of event divided by the number of patient-years of treatment-emergent surveillance for each treatment group. Patients can have more than one occurrence of each event.

Tabular summaries including numbers and percentages of the following adverse events will be provided:

- TEAEs;
- Serious TEAEs;
- TEAEs by SOC and PT;
- TEAEs by SOC, PT, and maximum severity;
- TEAEs by SOC, PT, and strongest relationship to study drug;
- TEAEs by decreasing frequency of PT;
- TEAEs of grade 3 or higher;
- TEAEs of grade 3 or higher by SOC, PT, and relationship to study drug;
- TEAEs related to study drug (judged by the investigator) by SOC, PT, and severity;
- TEAEs leading to study drug discontinuation;
- TEAEs leading to study drug discontinuation by SOC, PT, and severity;
- TEAEs leading to dose reduction;

- TEAEs leading to dose reduction by SOC, PT, and severity;
- TEAEs leading to dose interruption;
- TEAEs leading to dose interruption by SOC, PT, and severity;
- Serious TEAEs by SOC, PT, and severity;
- Serious TEAEs by SOC, PT, and relationship to study drug;
- Serious TEAEs that caused study treatment discontinuation by SOC and PT;
- TEAEs leading to death by SOC and PT.

Additionally, Kaplan-Meier methods will be used to display the time to the first grade 3 or higher TEAEs by treatment group.

Subgroup and supplemental tabulations of TEAEs by categorized treatment group, grade 3 and higher TEAEs by categorized treatment group, and serious TEAEs by categorized treatment group will be created as shown in Table 5.

Table 5: Subgroup and Supplemental Tabulations of Treatment-Emergent Adverse Events

Group Variable	Subgroups	Definition
Study Day Cut Points	
  ≤ 60 days after initiation of study drug  ≤ 180 days after initiation of study drug  ≤ 365 days after initiation of study drug  > 365 days after initiation of study drug 	
Adverse events will be assigned to day categories based on the treatment day of the start date (or worsening date) of the adverse event. Study days after initiation of study drug use the study day computations presented in Section 7.1.

Age (years)	
  < 65  ≥ 65  < 75  ≥ 75 	-
Baseline Body Mass Index	
  ≤ Median  > Median 	-
Geographic Region	
  North America  European Union  Rest of the World 	Defined in Appendix 2 .
History of Cardiovascular Disease	
  Yes  No 	Defined in Appendix 2 .

9.8.1.1. Adverse Events of Special Interest

The following TEAEs of special interests will be summarized for the overall safety population and by SOC and PT for each categorized treatment group. Additionally, for the following special adverse events, Kaplan-Meier methods will be used to display the time to the first occurrence of each of these events, if the number of events is deemed sufficiently large:

- Convulsions;
- Neutropenia;
- Cognitive and memory impairment disorders as identified by the higher-level group term for mental impairment;
- Hypertension;
- Hepatic impairment;
- Select cardiovascular events as defined in [Appendix 2](#);
- Posterior reversible encephalopathy syndrome (PRES).

A detailed list of the derivation of each term is provided in [Appendix 2](#).

9.8.2. Laboratory Assessments

Laboratory data in this study consist of hematology values, chemistry tests, and urine tests. Only data collected from the central laboratory during the treatment-emergent period will be summarized. Laboratory data collected outside the treatment-emergent period will only be listed in the data listings.

Normal ranges will be implemented to identify values that are outside the normal ranges and create the NCI toxicity grade using the CTCAE version 4.0. Parameters that have criteria available for both low and high values (e.g., hypercalcaemia for a high value of calcium and hypocalcaemia for a low value of calcium) will be summarized for both criteria (low and high). Patients will only be counted once for each criterion. The same patient can be counted for both criteria if the patient has laboratory values meeting each criterion. For each laboratory parameter, the baseline laboratory value is defined as the last laboratory value collected on or before the date and time of the first dose of study drug. The change from baseline to postbaseline value will be calculated for each laboratory parameter.

For laboratory parameters that are gradable by the CTCAE, a shift table will be provided for each parameter to summarize baseline toxicity grade versus worst postbaseline toxicity grade during the treatment-emergent period. The number and percentage of patients with at least 1 occurrence of grade 3 or grade 4 laboratory values in the treatment-emergent period will be summarized for each parameter and treatment group.

For each laboratory parameter that is not gradable by the CTCAE, a shift table based on the normal range (low, normal, and high) will be provided to summarize the baseline result versus both the lowest and the highest postbaseline result during the treatment-emergent period.

For patients with grade 3 and/or grade 4 laboratory values in the treatment-emergent period, a by-patient data listing will be presented to display data including visit label (eg, Week 17), assessment date (day), laboratory value, normal range flag (low, normal, and high), and change from baseline value. The baseline value will be flagged in this data listing.

The number and proportion of patients with liver test elevations will be presented by categorized treatment group. Liver function test elevations are assessed by using postbaseline results in ALT, AST, total bilirubin, and alkaline phosphatase during the treatment-emergent period based upon the definitions presented in [Table 6](#).

Table 6: Categories of Liver Test Elevations

Laboratory Test	Category
ALT, AST	Postbaseline result ≥ 3  upper limit of normal
	Postbaseline result ≥ 3  upper limit of normal and worse than baseline
	Postbaseline result ≥ 5  upper limit of normal
	Postbaseline result ≥ 10  upper limit of normal
	Postbaseline result ≥ 20  upper limit of normal
ALT or AST	Postbaseline result ≥ 3  upper limit of normal
Total Bilirubin	Postbaseline result ≥ 2  upper limit of normal
Alkaline Phosphatase	Postbaseline result ≥ 1.5  upper limit of normal

ALT, alanine aminotransferase; AST, aspartate aminotransferase.

The number and percent of patients with either ALT or AST ≥ 3 times the upper limit of normal and total bilirubin ≥ 2 times the upper limit of normal at concurrent and nonconcurrent visits will also be presented.

The number and percent of patients with either ALT or AST ≥ 3 times the upper limit of normal and total bilirubin ≥ 2 times the upper limit of normal with alkaline phosphatase < 2 times the upper limit of normal at concurrent visits will also be presented.

9.8.3. Vital Signs

Temperature, blood pressure (systolic and diastolic), and heart rate will be summarized at baseline and each subsequent scheduled assessment by treatment group as treated. Only data collected during the treatment-emergent period will be summarized. Baseline results are defined as the last vital sign results taken on or before the date and time of the first dose of study drug. Change from baseline will be calculated and presented for each parameter at all scheduled postbaseline assessment timepoints. The mean change from baseline and its

95% confidence interval for each treatment group and study visit will be plotted over time as well.

The number and proportion of patients experiencing potentially clinically significant abnormalities during the treatment-emergent period will be summarized by treatment group. The definitions of potentially clinically significant abnormalities are shown in [Table 7](#).

Table 7: Potentially Clinically Significant Abnormalities in Vital Signs

Parameter	Criteria for Potentially Clinically Significant Abnormalities
Systolic blood pressure	Absolute result ≥ 180 mm Hg and increase from baseline ≥ 40 mm Hg
	Absolute result ≤ 90 mm Hg and decrease from baseline ≥ 30 mm Hg
	Final visit or 2 consecutive visits results ≥ 10 mm Hg change from baseline
	Final visit or 2 consecutive visits results ≥ 15 mm Hg change from baseline
	Final visit or 2 consecutive visits results ≥ 20 mm Hg change from baseline
	Final visit or most extreme result ≥ 140 mm Hg
	Final visit or most extreme result ≥ 180 mm Hg
	Final visit or most extreme result ≥ 140 mm Hg and ≥ 20 mm Hg change from baseline
Diastolic blood pressure	Absolute result ≥ 105 mm Hg and increase from baseline ≥ 30 mm Hg
	Absolute result ≤ 50 mm Hg and decrease from baseline ≥ 20 mm Hg
	Final visit or 2 consecutive visits results ≥ 5 mm Hg change from baseline
	Final visit or 2 consecutive visits results ≥ 10 mm Hg change from baseline
	Final visit or 2 consecutive visits results ≥ 15 mm Hg change from baseline
	Final visit or most extreme result ≥ 90 mm Hg
	Final visit or most extreme result ≥ 105 mm Hg
	Final visit or most extreme result ≥ 90 mm Hg and ≥ 15 mm Hg change from baseline
Heart Rate	Absolute result ≥ 120 bpm and increase from baseline ≥ 30 bpm
	Absolute result ≤ 50 bpm and decrease from baseline ≥ 20 bpm

bpm, beats per minute; mm Hg, millimeters of mercury.

Appendix 1: Definition of Metastasis-Free Survival

Metastasis-free survival (MFS) is defined as time from randomization to radiographic progression as assessed by blinded independent central radiology review or death on study (death within 112 days of treatment discontinuation without evidence of radiographic progression), whichever occurs first.

The following table summarizes the protocol-specified rules for the radiographic evidence of progression (protocol version 4.0):

Tissue Type	Method of Assessment	Schedule	Comment
Bone	A whole-body radionuclide bone scan will consist of 5 regions including skull, thorax, spine, pelvis, and extremities. Radiographic progression for bone disease is defined as the appearance of 1 or more metastatic lesion on bone scan. When bone lesions are found in a single region, confirmation with a second imaging modality (plain film, CT, or MRI) will be required. Appearance of metastatic lesions in 2 or more of the 5 regions on a bone scan will not require confirmation with a second imaging modality.	Screening and every 16 weeks thereafter (earlier if progression is clinically suspected) until radiographic progression is confirmed by independent central radiology review	All study films should be read locally at the study site and submitted to the central imaging unit for independent central radiology review
Soft Tissue	Assessment of soft tissue disease will be done by CT or MRI. Radiographic progression for soft tissue disease is defined by RECIST 1.1.		

CT, computed tomography; MRI, magnetic resonance imaging; RECIST 1.1, Response Evaluation Criteria in Solid Tumors version 1.1.

The censoring rules for the primary and sensitivity analyses of MFS are summarized in the following table:

Analysis	Censoring Rules	Date of Censoring
Primary analysis of MFS	Patients with no baseline or no postbaseline assessments	Date of randomization
	Patients who were randomized but confirmed metastatic at baseline by independent central radiology review	Date of randomization
	Patients who had no confirmed metastasis as per independent central radiology review or did not die prior to data cutoff date	Date of the last radiographic assessment prior to data cutoff date
	Patients who had no confirmed metastasis as per independent central radiology review but died after 112 days following last dose of study drug	Date of the last radiographic assessment prior to data cutoff date
	Patients who initiate cytotoxic chemotherapy, abiraterone acetate, or nonradioactive bone-targeting agents without evidence of metastasis as per independent central radiology review	Date of the last radiographic assessment prior to first use of any such therapy
	Patients who experience a skeletal-related event without evidence of metastasis as per independent central radiology review	Date of the last radiographic assessment prior to the earliest skeletal-related event
	Patients with radiation therapy performed for prostate cancer-related lesions without evidence of metastasis as per independent central radiology review	Date of the last radiographic assessment prior to the earliest use of radiation therapy
	Patients with 2 or more consecutive missed tumor assessment visits without evidence of metastasis as per independent central radiology review	Date of the last radiographic assessment prior to the missed visit date
MFS Based on Investigator Assessment	Same as MFS	Same as MFS
Impact of Antineoplastic Therapies	All censoring rules for the primary analysis of MFS	Same as the primary analysis of MFS
	Patients who initiate any antineoplastic therapy without evidence of metastasis as per independent central radiology review	Date of the last radiographic assessment prior to first antineoplastic therapy use
Modified MFS 1 - Including Progression After Alternative Therapy as Event	Patients with no baseline or no postbaseline assessments	Date of randomization
	Patients who had no confirmed metastasis as per independent central radiology review but died after 112 days following last dose of study drug	Date of the last radiographic assessment prior to data cutoff date
	Patients who experience a skeletal-related event without evidence of metastasis as per independent central radiology review	Date of the last radiographic assessment prior to the earliest skeletal-related event

Analysis	Censoring Rules	Date of Censoring
	Patients with 2 or more consecutive missed tumor assessment visits without evidence of metastasis as per independent central radiology review	Date of the last radiographic assessment prior to the missed visit date
Modified MFS 2 – Including Post Treatment Deaths as event	Patients with no baseline or no postbaseline assessments	Date of randomization
	Patients who were randomized but confirmed metastatic at baseline by independent central radiology review	Date of randomization
	Patients who had no confirmed metastasis as per independent central radiology review or did not die prior to data cutoff date	Date of the last radiographic assessment prior to data cutoff date
	Patients who initiate cytotoxic chemotherapy, abiraterone acetate, or nonradioactive bone-targeting agents without evidence of metastasis as per independent central radiology review	Date of the last radiographic assessment prior to first use of any such therapy
	Patients who experience a skeletal-related event without evidence of metastasis as per independent central radiology review	Date of the last radiographic assessment prior to the earliest skeletal-related event
	Patients with radiation therapy performed for prostate cancer-related lesions without evidence of metastasis as per independent central radiology review	Date of the last radiographic assessment prior to the earliest use of radiation therapy
	Patients with 2 or more consecutive missed tumor assessment visits without evidence of metastasis as per independent central radiology review	Date of the last radiographic assessment prior to the missed visit date

ITT, Intent-to-treat; MFS, metastasis-free survival.

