5.4.2. Long-Term Follow-Up

All patients who permanently discontinue study treatment must have long-term follow-up as continuation of their every 16 weeks study visit schedule. Every reasonable effort must be made to obtain the required information. The long-term follow-up windows are ± 7 days.

Study site personnel may collect follow-up information by any means including telephone, during a patient’s clinic visit, chart review, or by communicating with referring healthcare providers for patients who do not return to the study site for their subsequent care.

Long-term follow-up procedures are listed in Table 7.

Table 7. Long Term Follow up Procedures

Activity / Assessment	Comment
General Activities (All Patients)	
Collect long-term follow-up information	Survival status. New antineoplastic therapies for prostate cancer. Opiate medications. Skeletal-related events (radiation therapy or surgery to bone, clinically apparent pathologic bone fractures, and spinal cord compression). Interventions due to locoregional progression (eg, radiation, transurethral resection of the prostate, nephrostomy tube placement).
Additional Assessments for Patients Who Do Not Have Confirmed Radiographic Progression at Time of Study Drug Discontinuation	
Radiographic assessments → Obtain approximately every 16 weeks or sooner if progression is clinically suspected until radiographic progression.	Use the same imaging modality as at screening. Radiographic imaging should be performed until radiographic progression is identified per Section 9.1.1 . A second imaging modality (plain film, CT, or MRI) will be required for confirmation of bone progression when bone lesions are found in a single region of the bone scan. Bone lesions in 2 or more of the 5 bone scan regions or soft tissue radiographic progression on the CT or MRI per RECIST 1.1 will not require confirmation. Determination of radiographic progression should be confirmed by independent central radiology review before stopping radiographic imaging.
BPI-SF, FACT-P, EQ-5D-5L and QLQ-PR25 questionnaires	Patient to complete these assessments if at the clinic.

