5. Must be within 42 days before randomization. Screening includes posteroanterior and lateral chest x-ray or chest CT scan, whole-body radionuclide bone scan, and abdominopelvic CT/MRI. If the screening bone scan shows a lesion suggestive of metastatic disease, the patient will be eligible only if a second imaging modality (plain film, CT, or MRI) excludes bone metastasis. If the imaging results are equivocal or consistent with metastasis, the patient is not eligible for enrollment. Use the same imaging method throughout the study.
6. Perform approximately every 16 weeks, but obtain images sooner if progression is clinically suspected. Radiographic imaging should be performed until radiographic progression is identified and confirmed by independent central radiology review per protocol. A second imaging modality (plain film, CT, or MRI) confirmation of bone progression is required when bone lesions are found in a single region on the bone scan.
7. If disease progression is suspected, perform imaging studies as appropriate.
8. Complete, sign, and fax the randomization authorization form to the medical monitor at the number provided on the form at least 2 business days before the day 1 visit.
9. Assess systems per standard of care at the study site and as clinically indicated by symptoms. Includes assessment of vital signs and weight (height only at screening).
10. Symptom directed and includes investigating any new abnormalities and assessment of vital signs.
11. Questionnaires will be completed for patients who come to the clinic.
12. Collect nonserious adverse event information from the time of first dose of study drug through safety follow-up. If no safety follow-up, collect adverse event information through 30 days after the last dose of study drug. Phone patients for follow-up if they do not come to the clinic.
13. May obtain at clinic visits, by phone contact, chart review, etc. Includes survival status, new antineoplastic therapies for prostate cancer, opiate use, skeletal-related events, and interventions due to locoregional progression.
14. Refer to the laboratory instruction manual for sample processing.

Study Period or Visit	Screening	Treatment			Unscheduled	Safety FU	Long-Term FU
Study Week	-4 to -1	1	5	17 Then Every 16	Varies [1]	Varies [2]	Every 16
Study Day	-28 to -1	1	29	113	na	na	na
Window (Days) [3]	na	na	±5	±5	na	±7	±7

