5. SAMPLE SIZE CONSIDERATIONS

The following assumptions are used in determining the sample size calculation for the MFS endpoint:

- 2:1 enzalutamide to placebo treatment allocation;
- An increasing nonuniform accrual of 0.25 patients per month per site with maximum accrual of 63 patients per month;
- For MFS a target hazard ratio of 0.72 at a 2-sided significance level of 0.05 with 90% power. Under an exponential model assumption, the target difference in Kaplan-Meier estimated median is 9 months (24 months versus 33 months). The median MFS of 24 months for the placebo group is based on published data.²

A total of 440 events provide 90% power to detect a target hazard ratio of 0.72 based on a 2-sided log-rank test and the overall significance level of 0.05. A sample size of approximately 1305 patients (870 enzalutamide and 435 placebo) will achieve 440 events. Approximately 10% of patients enrolled are expected to be lost to follow-up, will be found to have metastatic disease at study entry, or will have events censored due to required analytical methods, so approximately 1440 patients (960 enzalutamide and 480 placebo) will be enrolled. The time from date of first randomization until 440 MFS events are observed is estimated to be approximately 43 months.

Approximately 500 PSA progression events are expected at the time of the single MFS analysis. Based on a hazard ratio assumption of 0.60, this endpoint will have >95% power at a 2-sided significance level of 0.02 (see [Section 9.7.1](#) for details on multiplicity adjustments on key secondary endpoints).

Approximately 360 new antineoplastic therapy events are expected at the time of the single MFS analysis. This endpoint will have 80% power to detect a hazard ratio of 0.70 at a 2-sided significance level of 0.02 (see [Section 9.7.1](#) for details on multiplicity adjustments on key secondary endpoints).

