In this sensitivity analysis, patients who discontinue study drug primarily due to clinical deterioration (defined as drop out due to adverse event, defined by investigator) prior to protocol-defined evidence of radiographic progression will be considered as having clinical deterioration, and the date of such an event will be set as the date of study drug discontinuation. The approach used for the primary analysis of MFS will be repeated after accounting for these events. The hazard ratio and its 95% confidence interval will be reported.

In addition to these sensitivity analyses, the time to tumor assessment visits will be summarized by treatment groups using the median and its 95% confidence interval.

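### No planned MFS analysis cleanly lifts the censoring at skeletal-related events, so its effect on the hazard ratio cannot be read

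*SAP*

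**What the plan says.** The primary censoring table in SAP Appendix 1 has a row for "Patients who experience a skeletal-related event without evidence of metastasis as per independent central radiology review". Such men are censored at their last radiographic assessment before the earliest SRE, not at the SRE itself.

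The SAP does not define an SRE. The protocol does, in section 5.4.2 (Table 7): "Skeletal-related events (radiation therapy or surgery to bone, clinically apparent pathologic bone fractures, and spinal cord compression". That table belongs to long-term follow-up, and note 13 to the schedule in Protocol Appendix 5 describes the same follow-up item: "Includes survival status, new antineoplastic therapies for prostate cancer, opiate use, skeletal-related events". SAP 7.1 starts long-term follow-up on the day after the last day of study drug. The on-treatment visit tables (Protocol Tables 3 and 4) have no SRE item. They do require adverse-event and concomitant-medication review. Protocol 8.3.1 has worsening signs and symptoms of the cancer recorded as adverse events, and SAP 7.1 says all treatment modalities go on the concomitant medications page.

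SAP 9.7.2 describes Modified MFS 1 as also counting progression after the start of any prostate cancer treatment. For the clinical-deterioration analysis it says: "The approach used for the primary analysis of MFS will be repeated after accounting for these events". It also provides for progression and censoring reasons to be summarised by arm. Protocol 10.3.1 leaves to the SAP the sensitivity analyses that deal with possible competing risks for the assessment of progression.

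**The concern.** A pathologic fracture, a cord compression or palliative radiation to bone is plausibly a clinical sign of the bone disease that MFS is meant to detect. Protocol 1.1 itself links castration-resistant disease to bone metastases, fractures and cord compression. Censoring at the scan before such an event may remove men just as their risk of a confirmed metastasis rises, although imaging continues every 16 weeks until progression, on and off drug. If the share removed differs by arm, the primary hazard ratio shifts. A sensitivity analysis that lifts the rule would show by how much, and none does so cleanly.

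There are two further difficulties. Modified MFS 1 drops the separate radiation row so that progression after treatment counts, yet it keeps the SRE row, and an SRE by the protocol's definition includes radiation to bone. A man irradiated to bone therefore stays censored in the analysis meant to count his later progression. Also, the SAP does not say whether SREs come from the follow-up item alone or also from adverse-event and treatment records, so two programmers could derive different censoring dates from the same data.

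**Working it through.** **Step 1. The six MFS analyses side by side (SAP 9.7.2 and Appendix 1)**

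| Analysis | Status of the SRE row |
|---|---|
| Primary | Listed |
| Modified MFS 1 | Listed; the radiation and new-therapy rows are absent |
| Modified MFS 2 | Listed |
| Investigator assessment | Inherited (same rules as primary) |
| Impact of antineoplastic therapies | Inherited (all primary rules plus one) |
| Impact of clinical deterioration | No entry in Appendix 1; repeats the primary approach, adding discontinuation for an adverse event as an event |

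The last analysis could count an SRE that led to stopping drug. The SAP does not say whether that event or the earlier SRE censoring takes precedence, so it is not a clean test of the rule.

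**Step 2. The plan's own figure**

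Inputs from SAP section 5: "A total of 440 events provide 90% power to detect a target hazard ratio of 0.72 based on a 2-sided log-rank test"; "2:1 enzalutamide to placebo treatment allocation"; two-sided alpha 0.05.

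Schoenfeld events = (1.960 + 1.282)² / [(2/3)(1/3)(ln 0.72)²] = 10.51 / (0.2222 × 0.1079) = 439 after rounding up, against 440 stated. Power at 440 events is 0.901, against 0.90. The sample size is not in question. The hazard ratio at the two-sided 0.05 limit is exp(−1.96 / √(440 × 2/9)) = 0.82.

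**Step 3. Size of a possible shift**

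The documents give no SRE rate. Let qE and qP be the shares of would-be MFS events that SRE censoring removes on enzalutamide and placebo. With roughly exponential times and censoring close to the event, observed HR ≈ HR × (1 − qE)/(1 − qP). Taking 0.72 as the hazard ratio with those events counted:

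| qE | qP | Observed HR |
|---|---|---|
| 5% | 10% | 0.72 × 0.95/0.90 = 0.760 |
| 10% | 5% | 0.72 × 0.90/0.95 = 0.682 |
| 1% | 5% | 0.72 × 0.99/0.95 = 0.750 |
| 5% | 1% | 0.72 × 0.95/0.99 = 0.691 |
| equal | equal | 0.720 |

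With equal shares of 5% or 10%, 440 would-be events become 418 or 396, and power is 0.886 or 0.869. Since the analysis waits for about 440 counted events, the cost would fall on time rather than power. The placebo median of 24 months would read 24/0.95 = 25.3 or 24/0.90 = 26.7 months.

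**Step 4. Check of the formula**

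A small Cox simulation (1305 patients, 2:1, uniform 36-month accrual, 43-month cutoff, censoring up to 112 days before the event, 40 replicates) moved the HR from 0.727 to 0.757 for 1%/5% (enzalutamide/placebo), from 0.708 to 0.681 for 5%/1%, and from 0.724 to 0.723 for 5%/5%. The relative shifts agree with the formula. The assumed accrual gave about 520 to 540 events rather than 440, so this checks only the shift in the HR.

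**The case against.** The strongest case against has four parts.

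- **Recording.** A reader might infer that SREs are recorded only after study drug stops, so that a man on drug with the same event goes unrecorded. The documents do not support this. Only the dedicated item is confined to follow-up; a fracture, cord compression or bone radiation on treatment can reach the database as an adverse event or a treatment. What stands is that no source is named for the rule.
- **Visibility.** Censoring reasons will be summarised by arm, so an imbalance should show. That is true, and it answers any suggestion that the issue goes wholly unexamined. But a count does not give the hazard ratio under another rule.
- **Reach of the row.** Suspected progression prompts earlier scans, and unscheduled scans count, so some SREs will come with a centrally confirmed metastasis. The row might also be read as applying only to men who never progress. Modified MFS 1 points the other way: it lets progression after therapy count by dropping rows worded like this one, which implies that those rows discard later progression.
- **Size.** Shares of 5% to 10% are not in the documents. SAP section 5 allows about 10% for loss to follow-up, metastasis at entry and all analytic censoring together. Nor is it documented that time off drug differs by arm. This stands, so the figures are illustrations only.

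**Conclusion.** The point holds as a gap in the sensitivity analyses and in the definition of the censoring rule. All six MFS analyses list or inherit SRE censoring, none cleanly lifts it, and Modified MFS 1 keeps it against its own stated aim. The censoring is plausibly informative; the documents do not establish that it is.

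The effect depends on imbalance between arms, and neither its direction nor its size is known. Assumed shares of 5% and 10% in opposite arms would turn 0.72 into 0.68 or 0.76, and equal shares would leave it unchanged. A reader might infer that the primary estimate is biased in favour of enzalutamide, or that significance is at risk. The documents support neither: the shift can go either way, and 0.76 lies inside the limit of about 0.82 at 440 events. The issue is how far the estimated hazard ratio can be trusted, not whether the test was valid. The change is worth making because it is cheap.

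**What to change.** 1. Remove the SRE row from Modified MFS 1, so that it does what SAP 9.7.2 says. That alone does not isolate the SRE rule, because Modified MFS 1 lifts other rows too.
2. Add one supportive MFS analysis to SAP 9.7.2 and Appendix 1, in two versions.
   - (a) Primary rules with the SRE row lifted. For men with an SRE, also lift the radiation row and the bone-targeting-agent part of the new-therapy row from the SRE date onward; otherwise those rows would censor many of the same men. Later centrally confirmed progression or on-study death counts at its own date.
   - (b) As (a), but an SRE before central progression is an event at its date, limited to pathologic fracture, cord compression, and bone radiation or surgery for prostate cancer.
3. Define SRE in the SAP and use one derivation on and off drug, from the follow-up, adverse-event and concomitant-treatment pages, classified without reference to treatment arm.

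The cost is SAP wording, classification and programming on data already collected. There are two limits to state. Version (b) may still count some fractures not due to metastasis, possibly unevenly by arm, since Protocol 1.4 lists nonpathological fracture as an identified risk of enzalutamide; it should be read beside (a). And this SAP rests on the January 2018 protocol, after the 28 June 2017 cutoff and unblinding, and its section 8 plans no further analyses of the primary endpoint. The addition must therefore be labelled supportive and post hoc.
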